12.4 STUDY DISCONTINUATION CRITERIA34
12.4.1 STOPPING RULES FOR SAFETY REASONS34
12.4.2 RULES FOR DISCONTINUATION OF A SUBJECT34
13 REFERENCES35

List of Tables

Table 1. Schedule of Activities.....22

PROTOCOL SYNOPSIS

Financial Sponsor: Corcept Therapeutics, Inc.
Name of Finished Product: Mifepristone (Korlym)
Study Title: Mifepristone Dynamic Testing for Diagnosis for Central Adrenal Insufficiency
Study Phase: Phase II
Primary Objective: Phase I of the study is to determine whether recruitment at our institution is sufficient for a study for mifepristone use as a diagnostic tool to diagnose central adrenal insufficiency and to generate data to inform a post-pilot study. Phase II of the study involves taking those recruited and having them complete the study to generate the data.
Study Design: Single-center pilot feasibility study of mifepristone to evaluate the recruitment of participants with the diagnosis of confirmed or suspected secondary adrenal insufficiency. Cortisol (secondary endpoint), ACTH and other steroid responses (exploratory endpoints) to mifepristone in participants with normal insulin tolerance testing (ITT) and participants with confirmed or suspected adrenal insufficiency will be analyzed. The study will test primarily for feasibility of recruitment (phase 1) and provide preliminary data for planning a post-pilot study (phase 2).
Study Population: Subjects with normal ITT and subjects with confirmed or suspected diagnosis of central adrenal insufficiency.
1. Criteria for Inclusion and Exclusion: Please see section 4.
Test Product; Dose; and Mode of Administration: Single dose of mifepristone 600mg, administered orally
Reference or Placebo Therapy; Dose; and Mode of Administration: None
Duration of Treatment: One day
Variables: Cortisol, ACTH

Statistical Methods:

- For the primary endpoint of recruitment actual recruitment will be compared to target recruitment (1 patient per 6 weeks). Actual and target recruitment per month will be plotted and visually compared. Recruitment of ≥ 26 participants and study completion and complete data on ≥ 22 patients will be a success regarding the primary endpoint.
- For the secondary endpoint the day 2 cortisol level will be compared to the maximal ITT cortisol level to determine if and to what degree there is a correlation between the two measurements.
- Receiver operating characteristic (ROC) curve will be created with the day 2 cortisol level as the variable, and the ITT result as the “gold standard” test for adrenal insufficiency, to analyze the performance of cortisol as a diagnostic test.
- T-tests will be used to compare cortisol, ACTH, and other hormone levels between healthy individuals and those with diagnosed with central adrenal insufficiency.

1 INTRODUCTION

1.1 Indication

Central adrenal insufficiency (CAI) is the inadequate production of cortisol in the setting of physiologic stress. In contrast to primary adrenal insufficiency, CAI is due to pituitary or hypothalamic dysfunction. Today, CAI has a prevalence of roughly 150-280 per million.ⁱ The most common cause of CAI is administration of exogenous glucocorticoids. Other common pharmacologic causes of CAI include synthetic progestins and opiates, which can suppress the hypothalamic-pituitary-adrenal (HPA) axis. Primary pituitary pathologies include tumors, congenital or developmental causes, and hypophysitis. Brain trauma, radiation, and granulomatous diseases can also affect the neuroendocrine components of the (HPA) axis.

1.2 Background and Rationale

Central adrenal insufficiency can be challenging to diagnose, as patients often present with nonspecific symptoms of weakness, malaise, and nausea. Furthermore, patients with partial adrenal insufficiency may be asymptomatic until they encounter major physiologic stress. Currently, CAI is diagnosed with basal testing and/or dynamic testing. Basal testing that reveals low morning cortisol and ACTH suggests CAI. If basal testing is equivocal, dynamic testing is typically completed with cosyntropin stimulation test. Cosyntropin stimulation testing can diagnose or rule out primary adrenal insufficiency, but can also be equivocal in CAI. The gold standard for diagnosing CAI is dynamic testing with the insulin tolerance test (ITT); metyrapone testing is also used. ITT protocol requires administration of

insulin to induce hypoglycemia, followed by serial measurements of cortisol and ACTH response. However, ITT is uncomfortable for patients and poses risks associated with hypoglycemia, such as precipitation of cardiac events or seizures. Metyrapone testing is challenging, because it requires measurement of 11-deoxycortisol, and there is often cross-reactivity between 11-deoxycortisol with cortisol in commercial immunoassays.ⁱⁱ

Secondary adrenal insufficiency is a rare diagnosis and data on mifepristone use as a diagnostic tool is unavailable in these patients. Therefore, the current study will test recruitment of this population as the primary endpoint.

1.3 Hypothesis

With regards to the primary endpoint we propose that we can reach a target average recruitment of one patient every 6 weeks for a time study duration of 36 months.

With regards to the secondary endpoint we propose the use of mifepristone as an alternative dynamic testing reagent for CAI. Mifepristone is a glucocorticoid and progesterone receptor antagonist. In normal participants, mifepristone would be expected to cause a rise in morning cortisol. In subjects with CAI, morning cortisol will remain low. This alternative test would avoid patient discomfort associated with hypoglycemia required with insulin tolerance testing, and avoid the need to measure surrogate parameters, such as 11-deoxycortisol required with metyrapone testing.

1.4 Previous Human Experience

Mifepristone is a glucocorticoid and progesterone receptor antagonist. While it is well-known as an abortifacient agent, it is also used and FDA-approved for medical management of Cushing's syndrome. Prior studies have demonstrated that administration of mifepristone causes a dose-dependent increase in morning ACTH and cortisol starting at a dose of 4.5mg/kg.ⁱⁱⁱ Furthermore, the concurrent administration of mifepristone and evening dexamethasone 1mg resulted in normal morning ACTH and cortisol, indicating that mifepristone disinhibits HPA suppression by dexamethasone. Of note, these effects of mifepristone on ACTH and cortisol levels were only noted in hormone levels in the morning.

2 STUDY OBJECTIVES AND ENDPOINTS

2.1 Objectives

This study can be viewed as having two phases. The primary (first phase) objective of this pilot-feasibility study is to evaluate, whether recruitment of participants can be reached.

The secondary (phase II) objective is analysis of cortisol response to mifepristone in participants without history of adrenal insufficiency compared to participants with confirmed or suspected adrenal insufficiency. The cortisol response with mifepristone administration will be compared with the maximal cortisol response of the insulin tolerance test to determine whether there is any correlation between the two values.

Another objective of the study is to evaluate the effects of mifepristone on other steroid hormones and metabolites. The last objective is to determine whether there is a statistically large enough difference between the ACTH and cortisol response in healthy participants and those with adrenal insufficiency, to indicate that mifepristone could be used as an agent for diagnosis of central adrenal insufficiency.

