4 SUBJECT SELECTION

4.1 Subject Recruitment

The study population will include adult male and female patients (n = 20), who underwent ITT from 2012 to present, are scheduled to undergo ITT in the future, or are clinically suspected to have adrenal insufficiency.

Eligible participants will be identified through a EMERSE and Data Direct search of individuals who have undergone ITT between 2012 and present, who have ITT ordered to be completed, or who have adrenal insufficiency listed as a clinical diagnosis. In addition, eligible participants will be recruited through physician referral and through **review of clinic schedules listing individuals scheduled for ITT.**

Patients will be called and offered participation by the study staff.

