9.2 Data Analysis

9.2.1 *Analysis Populations*

As the primary endpoint recruitment will be analyzed as a primary endpoint. The cortisol response with mifepristone administration will be compared with the maximal ITT cortisol level in all patients as a secondary endpoint. In addition, the hormone levels of participants with normal ITT will be compared to those with confirmed diagnosis of central adrenal insufficiency. Data from this study will inform planning of a larger post-pilot study.

9.2.2 *Analysis of Primary Endpoint*

The primary endpoint of this pilot feasibility study is actual study participant recruitment. Reaching the target recruitment of one participant every 6 weeks over a 36-month period (target n=26) will be regarded successful in reaching the primary endpoint. We estimate an enrollment of 90% of patients in this study. This is in accordance with our prior experience in patients with rare diseases, who are often motivated regarding study participation. We estimate a total of 85% of patients with complete data as we only anticipate minimal study drop out due to side effects of the drug or non-analyzable specimens. Study recruitment will be plotted over time and actual and target recruitment will be visually compared. We will regard a total of 22 patients as a target in meeting the primary endpoint.

9.2.3 *Analysis of Secondary Endpoints*

The secondary data point is day 2 cortisol and ACTH response to mifepristone administration. The day 2 cortisol level will be compared to the maximal ITT cortisol level to determine if and to what degree there is a correlation between the two measurements. In addition, a receiver operating characteristic (ROC) curve will be created with the day 2 cortisol level as the variable, and the ITT result as the “gold standard” test for adrenal insufficiency, to analyze the performance of cortisol as a diagnostic test. The cortisol and ACTH values in participants with normal ITT will be compared to those with confirmed diagnosis of central adrenal insufficiency, using a

t-test to determine whether there is statistically significant difference between the two populations.

9.2.4 *Analysis of Secondary Endpoints*

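### The last objective in section 2.1 rests a statement on diagnostic use on a between-group difference, tested only by t-test, and is not linked to the ROC analysis already planned

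*Combined protocol and SAP*

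**What the plan says.** The last objective in section 2.1 looks for this result: "statistically large enough difference between the ACTH and cortisol response in healthy participants and those with adrenal insufficiency, to indicate that mifepristone could be used" for diagnosing central adrenal insufficiency. Neither that section nor any other gives the size of difference that would count.

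The between-group comparison is specified in section 9.2.3: "The cortisol and ACTH values in participants with normal ITT will be compared to those with confirmed diagnosis of central adrenal insufficiency", with a "t-test to determine whether there is statistically significant difference between the two populations". Section 9.2.4 applies the same test to ACTH and the other steroids. The synopsis, under Statistical Methods, says "T-tests will be used to compare cortisol, ACTH, and other hormone levels between healthy individuals and those with diagnosed with central adrenal insufficiency". No alpha, power, effect size or group split is stated for these tests.

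The plan also contains analyses that bear on diagnosis more directly:
- a ROC curve for day 2 cortisol against the ITT result (synopsis, 2.2.2, 7.2, 9.2.3);
- c-statistics for ACTH and the other steroids (2.2.3, 7.3);
- a hypothesis that the Pearson correlation between ITT peak cortisol and post-mifepristone cortisol exceeds 0.7 (2.2.2, 7.2).

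None of these carries a minimum AUC, sensitivity or specificity, and the last objective in 2.1 does not refer to them.

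**The concern.** Whether a test can be used for diagnosis depends on how far the values of affected and unaffected patients overlap. The null hypothesis of the t-test is that the group means are equal. It can be rejected when the means differ but the distributions still overlap too much for any cut-off to serve. Section 1.3 already predicts a mean difference, with cortisol rising in normal participants and staying low in central adrenal insufficiency, so rejecting equality adds little about classification.

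The documents say that the pilot will inform a post-pilot study. If the report follows the wording of 2.1, a significant group difference could be carried forward as support for diagnostic use, while the quantity that the next study needs for planning, classification accuracy with its uncertainty, is left without a stated role in that conclusion.

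**Working it through.** **The plan's own figures.** Section 9.2.2 sets one participant per 6 weeks over 36 months: 36 months is 156.5 weeks, and 156.5 / 6 = 26.1, which matches the target of 26. Then "We estimate a total of 85% of patients with complete data" gives 26 × 0.85 = 22.1, which matches "We will regard a total of 22 patients as a target in meeting the primary endpoint". Both reproduce. They are recruitment figures, and no sample size was derived for the t-test or for accuracy. Section 4.1 gives n = 20 instead, so 10/10 is also shown below.

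**Assumptions, none of them in the documents.** Normal values with equal SD in both groups, a two-sided 5% two-sample t-test, and 22 complete participants. The split between normal ITT and confirmed disease is unknown, so a range is used.

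**From AUC to standardised difference d.** Under this model AUC = Φ(d/√2), so d = √2 × Φ⁻¹(AUC). For AUC 0.80, d = 1.414 × 0.842 = 1.190. At the cut-off midway between the means, the share misclassified in each group is Φ(−d/2) = Φ(−0.595) = 0.276, about 28%.

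**Chance of a significant t-test at true AUC 0.80.** Noncentrality = d × √(n₁n₂/(n₁+n₂)), and the critical value with 20 degrees of freedom is 2.086.

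| Split | Noncentrality | Significant |
|---|---|---|
| 11/11 | 1.190 × √5.50 = 2.79 | 76% |
| 14/8 | 1.190 × √5.09 = 2.69 | 72% |
| 16/6 | 1.190 × √4.36 = 2.49 | 66% |
| 18/4 | 1.190 × √3.27 = 2.15 | 54% |

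With other totals the figure is 71% at 10/10 and 83% at 13/13.

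**Smallest observed difference that reaches significance at 11/11.** 2.086 × √(2/11) = 0.89 SD. That corresponds to an AUC of Φ(0.889/1.414) = 0.735, and to a sensitivity of Φ(0.889 − 1.282) = 35% at 90% specificity.

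**How the test responds to accuracy at 11/11.** Significance occurs in 5% of trials at true AUC 0.50, 57% at 0.75, 76% at 0.80 and 98% at 0.90.

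**What an AUC estimate would look like.** The Hanley-McNeil variance for AUC A with 11 per group uses Q₁ = A/(2−A) and Q₂ = 2A²/(1+A). At A = 0.80, Q₁ = 0.667 and Q₂ = 0.711, so the variance is [0.16 + 10 × (0.667 − 0.64) + 10 × (0.711 − 0.64)] / 121 = 0.0094 and the SE is 0.097. The approximate 95% interval is 0.80 ± 1.96 × 0.097, or 0.61 to 0.99.

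**A possible pass rule, checked.** Suppose the lower 95% limit of the AUC had to reach 0.80. Simulation at 11/11 with DeLong intervals on the logit scale shows that a marker with true AUC 0.90 would pass only about 12% of the time, or 16% if perfect separation counts as a pass.

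**The case against.** The strongest reply is that the documents contain no such decision rule. Section 2.1 names no test, the t-test sentence in 9.2.3 does not mention diagnosis, and the phrase in 2.1 can be read as a question about magnitude. Section 1.3 ties the proposal of mifepristone as an alternative test to the secondary endpoint, which is the correlation and the ROC analysis. The synopsis and 9.2.3 give the ROC curve the task of describing how cortisol performs diagnostically. A reader of the results would see the AUC beside the p-value. Recruitment is the primary endpoint, and no go/no-go decision depends on the t-test.

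Much of this stands, and it limits the consequence. A reader might infer that the plan declares the test usable whenever p < 0.05, or that it neglects classification. The documents support neither: the link from 2.1 to the t-test has to be inferred, and classification is analysed for both cortisol and ACTH. What remains is that 2.1 bases a statement on diagnostic use on a group difference, gives it no magnitude, and does not point to the ROC. If a magnitude was meant, it is missing.

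Two stronger numerical readings also fail. A reader might set the 76% against the nominal 5% and call it a false-positive rate. It is power under a true difference in means, and the t-test keeps its 5% under equality. A reader might also call the p-value uninformative. It is not, since rejection rises from 5% at AUC 0.50 to 98% at 0.90. It is a weak screen for accuracy.

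**Conclusion.** The point holds as a minor but real correction. The inference in 2.1, from a difference between groups to use in diagnosis, does not answer the classification question, and the analysis that does answer it is planned but not connected. Under the stated assumptions, a marker that misclassifies about 28% at the midpoint cut-off would give a significant t-test in 54% to 76% of trials with 22 participants, depending on the split. These figures illustrate the gap and do not predict the trial's result. Equal SD in particular is doubtful if cortisol rises in one group and stays low in the other, and the documents set no accuracy threshold by which 0.80 would be adequate or inadequate. The argument does not need a threshold, because a test of equal means sets no limit on overlap. The effect is confined to a non-primary objective of a recruitment-feasibility pilot.

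**What to change.** Reword the last objective in 2.1 along these lines: *to estimate how well day 2 cortisol (and, as an exploratory analysis, ACTH) classifies participants by ITT result, reported as the AUC with a 95% confidence interval, and sensitivity and specificity with exact 95% confidence intervals.*

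In 9.2.3 and the synopsis, add that any statement on diagnostic use rests on these estimates and their intervals, and that the t-tests are descriptive and reported as a mean difference with a confidence interval.

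Do not add a rule that the lower AUC limit must exceed 0.80. At this sample size it would reject most good markers, so the pilot should estimate and not pass or fail.

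The cost is wording in three places, with no new data, visits or participants. The downside is that the AUC interval will be wide with about 22 participants, so what the pilot can say about diagnostic use will be weaker than a significant p-value might suggest.

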2.2 Endpoints

2.2.1 Primary Endpoint

The primary endpoint of this pilot feasibility study is actual study participant recruitment. Reaching the target recruitment rate of one patient every 6 weeks over a 36-month period will be regarded as successful in reaching the primary endpoint.

2.2.2 Secondary Endpoint

The secondary endpoint is the correlation between the peak cortisol measured in ITT (the gold standard) and the cortisol measured the day after mifepristone administration. We will assess whether there is a strong relationship between ITT peak cortisol and the cortisol measured after mifepristone administration. We hypothesize that the Pearson's correlation coefficient (r) for this correlation will be > 0.7 . The results of the ITT will be regarded as the gold standard in the diagnosis of secondary adrenal insufficiency. As the true cut-off for diagnosis of adrenal insufficiency using post-mifepristone cortisol is unknown we will analyze the data using ROC c-statistics for different cut-offs.

2.2.3 Exploratory Endpoints

Exploratory endpoints include the impact of mifepristone on ACTH and other steroid hormones and metabolites, such as but not limited to corticosterone, aldosterone, androstenedione, 11-deoxycortisol, 11-deoxycorticosterone, DHEAS, DHEA, 17-hydroxyprogesterone, 17-hydroxypregnenolone. Analysis will be done by c-statistics in comparison the gold standard of ITT peak cortisol as well.

3 STUDY DESIGN

This will be a single-center trial of mifepristone to evaluate the ACTH and cortisol response to mifepristone in participants without history of adrenal insufficiency and participants with confirmed or suspected adrenal insufficiency. All adult participants who have undergone ITT from 2012 to present, are scheduled to undergo ITT in the future, or are clinically suspected to have adrenal insufficiency, will be approached for this study. There will be at least a one-week interval between ITT and mifepristone testing.

Subjects who meet inclusion criteria and agree to participation will undergo the study conducted over two days: baseline hormone labs will be obtained on the morning of day 1. A single dose of 600mg mifepristone is to be orally taken at 10PM on day 1. Participants will then return for repeat lab work on day 2.

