4.1.1 Inclusion Criteria

Adult (ages ≥ 18 years of age) male and female subjects who:

1. Completed ITT at University of Michigan from 2012 to present.
OR
2. Are scheduled to complete ITT.
OR
3. Are clinically suspected to have adrenal insufficiency but have not undergone ITT.

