5.3 Drug Supplies-Mifepristone

- Other names for the drug: KORLYM®, C1073, RU486
- Description: 300 mg tablets are light yellow to yellow, oval-shaped, film-coated tablets debossed with “Corcept” on one side and “300” on the other. Each bottle contains 28 tablets.
- Mode of action: Mifepristone is a selective antagonist of the progesterone receptor at low doses and blocks the glucocorticoid receptor (GR-II) at higher doses. Mifepristone has high affinity for the GR-II receptor but little affinity for the GR-I (MR, mineralocorticoid) receptor.

- Pharmacokinetics:

Absorption

Following oral administration of mifepristone to healthy volunteers, time to peak plasma concentrations of mifepristone occurred between 1 and 2 hours following single dose, and between 1 and 4 hours following multiple doses of 600 mg. The mean plasma concentrations of the three active metabolites of mifepristone peak between 2 and 8 hours after multiple doses of 600 mg/day, and the combined concentrations of the metabolites exceed that of the parent mifepristone. Exposure to mifepristone is substantially less than dose proportional. Time to steady state is within 2 weeks, and the mean (SD) half-life of the parent mifepristone was 85 (61) hours following multiple doses of 600 mg/day of mifepristone. Studies evaluating the effects of food on the pharmacokinetics of mifepristone demonstrate a significant increase in plasma levels of mifepristone when dosed with food.

Distribution

Mifepristone is highly bound to alpha-1-acid glycoprotein (AAG) and approaches saturation at doses of 100 mg (2.5 µM) or more. Mifepristone and its metabolites also bind to albumin and are distributed to other tissues, including the central nervous system (CNS).

Metabolism

Cytochrome P450 3A4 (CYP3A4) has been shown to be involved in mifepristone metabolism in human liver microsomes. Two of the known active metabolites are the product of demethylation (one monodemethylated and one di-demethylated), while a third active metabolite results from hydroxylation (monohydroxylated).

Elimination and Excretion

Excretion is primarily (approximately 90%) via the fecal route. Excretion in the urine accounts for less than 10%.

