6.2 Treatment Study Period

6.2.1 Visit 1 (Day 1)

Subject will be presented the consent document prior to any procedures on this day. Between 7AM and 9AM, baseline labs, including morning cortisol, ACTH, and other steroid hormones and metabolites (5ml serum, 5ml EDTA) and a serum pregnancy test will be obtained. A comprehensive metabolic panel and complete blood count will be obtained if not already performed in the prior 3 months. Patients will be provided a single dose of 600mg mifepristone to be administered orally, and subjects will be instructed to take the drug between 10PM and 11PM on Day 1. If the participant is scheduled for an ITT as part of their medical care and is consented for this study prior to completing ITT, the study team will attempt to obtain left over blood samples for measurement of baseline labs relevant for

mifepristone testing, if the serum is drawn before 10AM, the lab draw that is part of Day 1 of the study could be omitted in this scenario.

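### The one-week minimum between ITT and mifepristone fixes no test order and is not justified against the half-life the protocol reports, so an ITT used as reference may be done while drug remains

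*Combined protocol and SAP*

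**What the plan says.** Section 3 sets the spacing: "There will be at least a one-week interval between ITT and mifepristone testing". Footnote a to Table 1 repeats it. Neither place gives an order or a reason for choosing a week.

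Section 4.1.1 offers three entry routes:

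- Criterion 1: "Completed ITT at University of Michigan from 2012 to present". These participants are always ITT-first.
- Criterion 2: "Are scheduled to complete ITT".
- Criterion 3: "Are clinically suspected to have adrenal insufficiency but have not undergone ITT".

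The only text that describes a sequence is in section 6.2.1. For a participant consented before a planned clinical ITT, "the study team will attempt to obtain left over blood samples for measurement of baseline labs relevant for" the mifepristone test, and the Day 1 draw may then be skipped. This implies ITT first in that case, but as an option and not a requirement.

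On the drug, section 3 says: "A single dose of 600mg mifepristone is to be orally taken at 10PM on day 1". Section 5.3 reports that "the mean (SD) half-life of the parent mifepristone was 85 (61) hours following multiple doses of 600 mg/day of mifepristone" and, for the three active metabolites, that "the combined concentrations of the metabolites exceed that of the parent mifepristone".

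Sections 2.2.2 and 7.2 make the ITT the reference standard. Its peak cortisol is one of the two variables in the correlation (hypothesised r above 0.7). Under section 9.2.3 its result is the reference for the ROC curve. The t-tests in sections 9.2.3 and 9.2.4 set participants with a normal ITT against those with confirmed central adrenal insufficiency. Section 9.2.1 applies the cortisol comparison to every patient, without regard to test order.

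**The concern.** The index test and its reference should be measured independently. Here the index test is a drug that section 1.3 expects to raise morning cortisol in normal participants, and the reference is itself a cortisol measurement. If the drug is given first and is still present at the ITT, the index test could alter the reference against which it is judged.

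That would bear on three analyses: the correlation, the ROC curve and the comparison of ITT-defined groups. Section 9.2.2 targets 22 participants with complete data, so one affected pair would be 1/22 = 4.5% of the pairs if all 22 had an ITT, and a larger share if fewer did. These results are meant to inform a post-pilot study. If the order is not recorded and reported, a reader of the results cannot tell whether carry-over was possible.

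**Working it through.** **The plan's own figure.** The one-week minimum has no stated inputs or washout calculation, so there is nothing to reproduce. The check is what the week implies under the pharmacokinetics that the protocol reports.

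**Inputs.**

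- Minimum interval: one week = 168 h (section 3; Table 1, footnote a).
- Parent half-life: mean 85 h, SD 61 h, after multiple doses (section 5.3). One SD either side gives 85 − 61 = 24 h and 85 + 61 = 146 h.
- Single-dose half-life: not given. Metabolite half-lives: not given.

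**Formula.** Assuming first-order elimination, the fraction remaining at time t is 0.5^(t / half-life).

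**Results at 168 h.**

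| Half-life | Half-lives elapsed | Parent drug remaining |
|---|---|---|
| 24 h (mean − 1 SD) | 168/24 = 7.0 | 0.8% |
| 85 h (mean) | 168/85 = 1.98 | 25.4% |
| 146 h (mean + 1 SD) | 168/146 = 1.15 | 45.0% |

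**Sensitivity to the start of the week.** The documents do not say whether the week runs from Day 1 or Day 2. With a 10 PM dose and an ITT assumed at 8 AM, one week from Day 1 is 6 × 24 + 10 = 154 h after the dose, and one week from Day 2 is 7 × 24 + 10 = 178 h. At the mean half-life these leave 28.5% and 23.4%. The choice matters little beside the spread in half-life.

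**Who can be affected.** Criterion 1 entrants cannot, because their ITT is already done. Criterion 2 entrants can, unless the ITT happens to come first. Criterion 3 entrants can only if a clinical ITT follows: Table 1 schedules none, and without one they contribute no pair. The documents give no count of mifepristone-first pairs.

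**The case against.** The strongest objection is that drug present is not the same as ITT altered. Section 1.4 describes a dose-dependent rise in ACTH and cortisol beginning at 4.5 mg/kg, and only in morning levels. Section 5.3 says that glucocorticoid-receptor blockade occurs at the higher doses. On the decay above, 25.4% of 600 mg is about 152 mg, which is below 4.5 mg/kg for anyone heavier than 152/4.5 ≈ 34 kg. The 45% case is 270 mg, which is below it for anyone heavier than 270/4.5 = 60 kg. The documents say nothing about an effect of the drug on a hypoglycaemia-stimulated peak.

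Much of this stands: an effect on ITT peak cortisol is unproven. It does not settle the matter the other way. Treating residual drug as a fresh dose of the same size is crude, because section 5.3 reports active metabolites that together exceed the parent and exposure that rises less than in proportion to dose. That last point also makes simple decay approximate. The morning-only limit does not remove the concern either, since section 6.2.1 allows for ITT blood drawn before 10 AM.

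A reader might also infer that sections 3 and 5.3 contradict each other. They do not. One sets a spacing, the other reports pharmacokinetics from multiple dosing, and the week is never presented as a washout. The supportable statement is that the interval is not justified against the reported half-life.

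Finally, the only sequence the protocol describes for people with a scheduled ITT is ITT first, so mifepristone-first pairs may be few or absent. That is fair, but the wording permits them and the analysis would pool them.

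**Conclusion.** The point holds as a gap in design and analysis. The spacing rule has no direction, section 4.1.1 admits people whose ITT is still to come, and section 9.2 makes no distinction by order. An ITT one week after mifepristone would follow the plan with about 25% of the parent drug remaining (0.8% to 45% over one SD either side). This rests on first-order decay and on applying the multiple-dose half-life to a single dose.

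A reader might go further and conclude that the correlation, the ROC curve and the patient classification will be biased. The documents do not support that: they show neither an effect of residual drug on ITT peak cortisol nor any mifepristone-first pair. The direction and size of any bias are unknown. The exposure is confined to the secondary and exploratory analyses that use the ITT; the primary endpoint, recruitment, is unaffected. The point still deserves action because the protection is cheap and depends on data that should be captured during the study.

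**What to change.** - Reconcile section 3, section 4.1.1, section 5.3, section 6.2.1 and footnote a of Table 1 on the order of the two tests and the basis for the interval. No interval is proposed here; that is for the sponsor and the investigator.
- Record, for every pair, which test came first and the gap in days.
- In section 9.2.3, report the correlation and the ROC analysis for ITT-first pairs, show any mifepristone-first pairs separately, and give the all-pairs analysis alongside. No data are then discarded, and a reader can see whether order matters.

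The cost is a few sentences of wording, two recorded items per participant and a little more analysis work. The downside is slightly fewer pairs in the ITT-first analysis. If every pair proves to be ITT-first, the analyses coincide and nothing is lost.
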